11.11 Appendix 11. Response Evaluation Criteria in Solid Tumors (RECIST) Version 1.1

Quick Reference

This study utilizes RECIST 1.1 criteria. Details of implementation of the criteria will be provided in the site reader web-based training.

Definitions

• Measurable Lesions

- **Measurable Tumor Lesions** – Non-nodal lesions with clear borders that can be accurately measured in at least 1 dimension with longest diameter ≥ 10 mm in CT/MRI scan with slice thickness no greater than 5 mm. When slice thickness is greater than 5 mm, the minimum size of measurable lesion should be twice the slice thickness.
- **Nodal Lesions** - Lymph nodes are to be considered pathologically enlarged and measurable, a lymph node must be ≥ 15 mm in short axis when assessed by CT/MRI (scan slice thickness recommended to be no greater than 5 mm). At baseline and in follow-up, only the short axis will be measured and followed.
 - Nodal size is normally reported as 2 dimensions in the axial plane. The smaller of these measures is the short axis (perpendicular to the longest axis).
- **Irradiated Lesions** - Tumor lesions situated in a previously irradiated area, or in an area subjected to other loco-regional therapy, are not measurable unless there has been demonstrated progression in the lesion prior to enrollment.

• Non-measurable Lesions

- All other lesions, including small lesions (longest diameter < 10 mm or pathological lymph nodes with ≥ 10 mm but to < 15 mm short axis with CT scan slice thickness no greater than 5 mm) are considered non-measurable and characterized as non-target lesions.
- Other examples of non-measurable lesions include:
 - Lesions with prior local treatment: tumor lesions situated in a previously irradiated area, or an area subject to other loco-regional therapy, should not be considered measurable unless there has been demonstrated progression in the lesion.
 - Biopsied lesions
 - Categorically, clusters of small lesions, bone lesions, inflammatory breast disease, and leptomeningeal disease are non-measurable.

Methods of Measurement

- **Measurement of Lesions** - The longest diameter of selected lesions should be measured in the plane in which the images were acquired (axial plane). All measurements should be taken and recorded in metric notation. All baseline evaluations should be performed as closely as possible to the beginning of treatment and not more than 4 weeks before study day 1.
- **Methods of Assessment** - The same method of assessment and the same technique should be used to characterize each identified and reported lesion throughout the trial.
- **CT/MRI** – Contrast-enhanced CT or MRI should be used to assess all lesions. Optimal visualization and measurement of metastasis in solid tumors requires consistent administration (dose and rate) of IV contrast as well as timing of scanning. CT and MRI should be performed with \leq 5 mm thick contiguous slices.

Baseline documentation of “Target” and “Non-target” lesions

- **Target Lesions** - All measurable lesions up to a maximum of two (2) lesions per organ and five (5) lesions in total, representative of all involved organs should be identified as target lesions and recorded and measured at baseline.
 - Target lesions should be selected on the basis of their size (lesions with the longest diameter) and suitability for accurate repeated measurements.

Pathologic lymph nodes (with short axis \geq 15 mm) may be identified as target lesions.

All other pathological nodes (those with short axis \geq 10 mm but $<$ 15 mm) should be considered non-target lesions.

11.12 Appendix 12. Immune Response Evaluation Criteria in Solid Tumors (iRECIST)

Immune Response Evaluation Criteria in Solid Tumors (iRECIST) (Seymour et al, 2017) is a modification of RECIST 1.1 (Eisenhauer, et al., 2009) for use in cancer immunotherapy trials. The RECIST working group published iRECIST to address response patterns specific to immunotherapies, including late and durable responses after having met PD according to RECIST 1.1.

The present document is not meant to be an exhaustive teaching tool on iRECIST. Instead it is meant to outline the concepts and differences between iRECIST and RECIST 1.1.

The tumor evaluations are exactly the same for RECIST 1.1 and iRECIST, except for the timepoint response nomenclature, until PD has been reached. For example, if a PR is identified at timepoint 2 for RECIST 1.1, this is called iPR at the same timepoint with the exact same measurements utilized. Only when the patient reaches RECIST 1.1 PD do the timepoint assessment processes begin to differ.

iRECIST Disease Categories

The iRECIST criteria define measurable disease, non-measurable disease, target-lesions, and non-target lesions using RECIST 1.1 definitions:

- Measurable lesions:
 - Non-nodal lesions must be ≥ 10 mm in the longest diameter
 - Nodal lesions must be ≥ 15 mm in the longest diameter
- A maximum of five measurable lesions (two per organ) can be target lesions
- All other disease is considered non-target (nodal lesions must be ≥ 10 mm in the short axis to be considered pathological)

At baseline, disease is categorized as target or non-target per RECIST 1.1. The same definitions and measurement types are applied to iRECIST assessments. Target lesions are measured uni-dimensionally and non-target lesions are assessed qualitatively.

New lesions are identified per RECIST 1.1 definitions, but are further categorized per iRECIST as new target lesions and new non-target lesions:

- New iRECIST target lesions must measure ≥ 10 mm in longest diameter (new nodal lesions must be ≥ 15 mm in the short axis)
- All other new iRECIST lesions are new non-target lesions (nodal lesions must be ≥ 10 mm in short axis to be considered pathological)

iRECIST recommends measuring up to five new target lesions. The requirement to measure new lesions starts at the time point of RECIST 1.1 PD. Measurement of more than five new lesions is optional and considered exploratory.

iRECIST Calculations

The iRECIST criteria requires the calculation of target lesion sum of measures (SOM) and new target lesion sum of measures (SOM). These are 2 distinct sums:

- **Target lesion SOM** is calculated by summing the longest diameter of target lesions (and/or short axis of target nodes). **Note:** This is the same calculation performed for RECIST 1.1 and labeled sum of diameters (SOD).
- **New target lesion SOM** is calculated by summing the longest diameter of new target lesions (and/or short axis of new target lesion nodes).

Tumor Response Assessment

The prefix “i,” meaning immune, is used to differentiate iRECIST responses from RECIST 1.1 responses.

The overall response at the time point of RECIST 1.1 PD is assessed as immune unconfirmed progressive disease (iUPD) per iRECIST initiating application of the iRECIST criteria.

After the initial iUPD assessment per iRECIST, the following guidelines apply:

- iUPD → followed by tumor shrinkage = iCR, iPR, or iSD
- iUPD → followed by worsening = iCPD
- iUPD → followed by no change = iUPD

When iUPD is followed by tumor shrinkage, this is referred to as “resetting the bar” and is 1 of the most important concepts of iRECIST. A subject cannot be assessed as iCPD at the time point immediately after “resetting the bar.” Disease must again qualify for iUPD, then worsen to be assessed as iCPD.

iRECIST tumor response assessments of iCR and iPR are made with reference to the original baseline time point for the subject, acquired during the study screening period. The nadir, or a subject’s best response on study, is used as the comparator when assessing for iUPD. iCPD is assessed with reference to the iUPD assessment being confirmed.

Target Lesion Assessments

The table within this section defines target lesion assessments per iRECIST.

Table 11-9. iRECIST Target Lesion Assessments

iRECIST Target Lesion Assessments	Requirements
Immune Complete Response (iCR)	Requires disappearance of all non-nodal target lesions and normalization of pathological target lymph nodes to <10 mm in short axis
Immune Partial Response (iPR)	Requires $\geq 30\%$ decrease in sum of measures of target lesions, taking as reference the baseline target lesion sum 
• The reference time point is the subject's original baseline time point acquired during the study screening period
Immune Unconfirmed Progressive Disease (iUPD)	Requires $\geq 20\%$ and a ≥ 5 mm increase in the sum of measures of target lesions, taking as reference the nadir time point 
• The nadir time point is the time point with the smallest target lesion sum on study, including pre RECIST 1.1 PD time points
Immune Stable Disease (iSD)	When the requirements for iCR or iPR are not met, in the absence of iUPD
Immune Confirmed Progressive Disease (iCPD)	A target lesion assessment of iCPD requires worsening of target lesions as evidenced by an increase of ≥ 5 mm in the target lesion SOM with reference to an immediately prior target lesion assessment of iUPD.

Non-Target Lesion Assessments

The table within this section defines non-target lesion assessments per iRECIST.

Table 11-10. iRECIST Non-target Assessments

iRECIST Non-Target Lesion Assessments	Requirements
Immune Complete response (iCR)	Requires disappearance of all non-nodal non-target lesions and normalization of pathological non-target lymph nodes to <10 mm in short axis
Immune Unconfirmed Progressive Disease (iUPD)	Requires unequivocal progression of non-target lesions
Non-iCPD/non-iUPD	Requires persistence of 1 or more non-target lesions and not meeting the non-target lesion requirements for iCR or iPD
Immune Confirmed Progressive Disease (iCPD)	Requires worsening of non-target lesions in comparison to an immediately prior non-target lesion assessment of iUPD.

New Lesions

New lesions that meet the RECIST 1.1 definition of a target lesion (non-nodal ≥ 10 mm in longest diameter or nodal ≥ 15 mm in the short axis) are categorized as new target lesions. iRECIST recommends measuring up to five new target lesions and that other new lesions are categorized as new non-target lesions (nodal lesions must be ≥ 10 mm in short axis to be considered pathological).

A separate sum, the SOM of new lesions, is calculated by taking the sum of new target lesion measurements. After first appearance, new lesions can worsen, remain unchanged, or disappear. If the SOM of new target lesions increases by ≥ 5 mm, there is unequivocal worsening of new non-target lesions, or appearance of additional new lesions this is considered worsening. Otherwise, the persistence of new lesions is considered unchanged.

Overall response

The first table within this section defines overall response assessments per iRECIST. The second table provides further detail on confirmation of progressive disease ie, the assessment of iCPD.

Table 11-11. iRECIST Overall Response

iRECIST Target Lesion Assessments	Requirements
Immune Complete Response (iCR)	
 Can only be assessed after the initial iRECIST iUPD time point (ie, the time point of RECIST 1.1 PD) Requires all of the following: 
 Disappearance of all non-nodal target lesions and normalization of pathological target lymph nodes to <10 mm in short axis – if any were present Disappearance of all non-nodal non-target lesions and normalization of pathological non-target lymph nodes to < 10 mm in short axis – if any were present No new lesions can appear for the first time or persist. Any previously identified new lesions must have disappeared.
Immune Partial Response (iPR)	
 Can only be assessed after the initial iRECIST iUPD time point (ie, the time point of RECIST 1.1 PD) Requires all of the following: 
 $\geq 30\%$ decrease in sum of measures of target lesions with reference to the baseline target lesion sum The reference time point is the subject's original baseline time point acquired prior to drug initiation Non-target persistence without worsening or non-target complete resolution No new lesions can appear for the first time. No worsening of new lesions. Persistent new lesions can be present if unchanged.
Immune Unconfirmed Progressive Disease (iUPD)	
 Always assessed at the time point of RECIST 1.1 PD (ie, the initial iRECIST iUPD time point), can also be assessed after RECIST 1.1 PD Requires any of the following: 
 $\geq 20\%$ and a ≥ 5 mm increase in the sum of measures of target lesions, with reference to nadir time point (ie, the time point with the smallest target lesion sum on study) The reference time point is the time point with the smallest target sum since (and including) the original baseline Unequivocal progression of non-target lesions First appearance of new lesions
Immune Stable Disease (iSD)	
 Can only be assessed after the initial iRECIST iUPD time point (ie, the time point of RECIST 1.1 PD) Is assessed when the requirements for iCR or iPR are not met, in the absence of iUPD
Immune Confirmed Progressive Disease (iCPD)	See Table 11-12

Table 11-12. iCPD Requirements Summary

Immune Confirmed Progressive Disease (iCPD) Requirements	
An overall response of iCPD can only be assessed immediately after a time point with overall response of iUPD ¹	
Cause of iUPD	iCPD Requirements
Target Lesion Progression	Additional worsening of target lesions as evidence by an increase of $\geq 5\text{mm}$ in the target lesion SOM
Non-Target Lesion Progression	Any worsening in non-target lesions
New Target Lesions	Additional worsening of new target lesions as evidenced by an increase of $\geq 5\text{mm}$ in the new target lesion SOM, or additional new target lesions
New Non-Target Lesions	Any worsening in non-target lesion lesions or additional non-target new lesions
Any cause	New RECIST 1.1-assigned progression in another lesion category (ie, target or non-target lesions reach the definition of iUPD for the first time per Table 1 or Table 2, or there are new lesions for the first time)

¹ Or immediately after an assessment of UE, NA, or ND if the assessment immediately before was iUPD

- Unable to evaluate (UE): Any lesion present at baseline which was not assessed or was unable to be evaluated leading to an inability to determine the status of that particular tumor for that time point
- Not Available (NA): Scan not available
- Not Done (ND): Radiographic imaging was not performed at this time point to evaluate the target lesions

Best Overall Response

Immune Best Overall Response (iBOR) is determined for iBOR as follows:

- iBOR is the best response seen since iUPD
- iBOR does not require confirmation
- For an iBOR of progression, the time point of iUPD that turned into iCPD is the time point of iBOR

Special cases

Bone lesions, cystic lesions, lesions with prior treatment, fluid collections, merging lesions, and splitting lesions are given special mention within the RECIST 1.1 publication. These considerations should also be applied to iRECIST.

Methods of Assessment and Image Acquisition Specifications

For each subject at each timepoint, there is a separate RECIST 1.1 assessment and iRECIST assessment. Until PD has been reached, these assessments rely on the same measurements and NT/new lesion assessments. Subsequently, the assessments will differ as described above. Image acquisition for a subject should be kept consistent for the entire time the subject is on trial, including for the post RECIST 1.1 PD time points, which are assessed by iRECIST.

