8.2.2 Efficacy Assessments

Efficacy will be determined by both clinical laboratory values and radiographic assessments (as outlined in Section [3](#)).

Radiographic Assessments

Radiographic assessments will be obtained as scheduled in [Table 1-3](#) irrespective of cycle duration including dose delays and treatment discontinuation. Standard radiological assessments should take place until clinically significant disease progression or deterioration, withdrawal of consent, or start of new anticancer therapy. Every assessment must include contrast-enhanced CT of the chest, abdomen, pelvis, and all other known sites of disease. The assessment should include MRI of the brain if a subject has signs or symptoms suggestive of CNS metastases. The assessment can be conducted earlier if clinical deterioration necessitates an earlier scan at the discretion of the managing physician. The same contrast and modality used at screening should be used for all subsequent assessments.

Tumor burden assessments will be performed based on RECIST 1.1 and iRECIST. RECIST 1.1 criteria will be used to determine eligibility based on the investigator's review of the radiographic data. Although tumor assessments following RECIST 1.1 will continue through the first disease progression (PD), iRECIST will be used and documented in eCRF to account for unique tumor response characteristics observed with immunotherapies and enable treatment decisions beyond progression (per RECIST 1.1). Tumor burden assessment performed at sites for decisions on treatment continuation will be based on iRECIST only and will continue until immune Confirmed Progression Disease (iCPD). Tumor burden assessments by the central core laboratory will be based on RECIST 1.1 and iRECIST. To confirm disease progression, a second CT scan must be performed 4-8 weeks after the first detection of radiographical progression. Responses (partial response [PR] and complete response [CR]) require confirmation by a repeat consecutive assessment at least 4 weeks after the first detection of radiographical response. Refer to the imaging manual for details on imaging assessments.

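### Appendix 12 classifies an unchanged new lesion after iUPD in two ways (iUPD in its text, iSD in Table 11-11), and the table then leaves no route to confirm progression from that lesion

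*Protocol*

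**What the plan says.** Protocol Section 11.12 (Appendix 12) sets the iRECIST rules in several places.

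- **Text, Tumor Response Assessment.** After the first iUPD, the transitions are iUPD "followed by no change = iUPD" and iUPD "followed by worsening = iCPD". Only shrinkage leads to iCR, iPR or iSD, and after such a reset "Disease must again qualify for iUPD, then worsen to be assessed as iCPD".
- **Text, New Lesions.** Three findings count as worsening: a rise of at least 5 mm in the sum of new target lesions, clear worsening of new non-target lesions, or additional new lesions. "Otherwise, the persistence of new lesions is considered unchanged".
- **Table 11-11, iUPD row.** Any one of three findings is needed: a target sum at least 20% and 5 mm above nadir; "Unequivocal progression of non-target lesions"; or "First appearance of new lesions".
- **Table 11-11, iSD row.** "Is assessed when the requirements for iCR or iPR are not met, in the absence of iUPD".
- **Table 11-11, iPR row.** A known new lesion may be present if unchanged, but not if it has worsened.
- **Table 11-12.** iCPD can be given only at the time point following an iUPD; unevaluable or missing scans may lie between.

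Section 8.2.2 gives these labels a use: "Tumor burden assessment performed at sites for decisions on treatment continuation will be based on iRECIST only", and these assessments run until iCPD. The central core laboratory reads by both RECIST 1.1 and iRECIST.

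**The concern.** A new lesion appears once. At the next scan it is no longer a first appearance, so if it is unchanged and the targets are stable it meets no iUPD criterion in Table 11-11 and falls to iSD. The text calls the same finding no change and keeps iUPD. The difference carries forward, because iCPD must follow iUPD directly: once the table has given iSD, later growth of that lesion cannot be confirmed and cannot restart iUPD either.

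There is also a gap that does not depend on the text and table disagreeing. The table allows iPR with an unchanged new lesion. If that lesion then grows, iPR is excluded, but no iUPD criterion covers the growth, so iSD is the only label left.

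Three things are at stake. Site and core laboratory readers could label identical scans differently. The best overall iRECIST response, defined in Appendix 12 as the best seen since iUPD, could be iSD by one reading and not by the other. And a subject with an iPR could have no progression date from a lesion that is plainly growing, which matters for the iRECIST duration of response planned in Protocol Section 9.4.2.2.

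**Working it through.** The plan states no figure to reproduce. The check applies the two sets of rules to the same hypothetical scans.

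**Inputs.** From Appendix 12: the criteria listed above. From Table 1-3: scans every 6 weeks to week 12, then every 8 weeks, so weeks 6, 12, 20 and 28. From Section 8.2.2: progression is confirmed by a scan 4 to 8 weeks later. Assumed for illustration: baseline target sum 50 mm, a first new lesion of 12 mm, no non-target progression.

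**Thresholds.** iPR needs a target sum of at most 0.70 × 50 = 35 mm. With a nadir of 50 mm, target iUPD needs at least 1.20 × 50 = 60 mm (a rise of 10 mm, so the 5 mm condition is also met).

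| Target sum (mm) | New-lesion sum (mm) | Tables 11-11 and 11-12 | Text |
|---|---|---|---|
| 50, 50 | 12, 18 | iUPD, iCPD | iUPD, iCPD |
| 50, 50 | 12, 12 | iUPD, **iSD** | iUPD, **iUPD** |
| 50, 50, 50 | 12, 12, 18 | iUPD, **iSD, iSD** | iUPD, **iUPD, iCPD** |
| 50, 62 | 12, 12 | iUPD, iCPD | iUPD, iCPD |
| 50, 50, 62, 68 | 12 throughout | iUPD, iSD, iUPD, iCPD | iUPD, iUPD, iCPD at the third scan |
| 62, 62 | none | iUPD, iUPD | iUPD, iUPD |

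**Third row in detail.** At week 12 the target is 0% above nadir, 50 mm exceeds 35 mm so there is no iPR, and the new lesion is not a first appearance. The table gives iSD; the text gives iUPD. At week 20 the new lesion has risen 18 − 12 = 6 mm, which is at least 5 mm and so is worsening. By the text this follows iUPD and is iCPD. By the tables it follows iSD, so iCPD is barred, and no iUPD criterion is met.

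The last row shows that the conflict is specific to new lesions: target progression is measured against nadir, so an unchanged target sum stays iUPD under both rules.

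**Growth after iPR.** Take target sums of 32.5, 30, 30 and 30 mm (−35%, then −40%) with a new lesion of 12, 12, 30 and 45 mm.

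- Week 6: first appearance, iUPD.
- Week 12: 30 mm is at most 35 mm and the new lesion is unchanged, iPR.
- Week 20: the lesion rises 30 − 12 = 18 mm. iPR is excluded, the target is 0% above its nadir, nothing appears for the first time: iSD.
- Week 28: a further 45 − 30 = 15 mm, again iSD.

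The text requires disease to qualify for iUPD again but does not say how growth of a known new lesion would do so.

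**Delay.** In the fifth row the text gives iCPD at week 20 and the tables one scan later: 4 to 8 weeks. In the iPR sequence, if the week 20 growth counted as iUPD, confirmation would fall at weeks 24 to 28 (20 + 4 to 20 + 8). If instead a different event at week 28 had to start iUPD, confirmation would fall at weeks 32 to 36. The difference is 32 − 24 = 36 − 28 = 8 weeks.

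**The case against.** The best defence is a harmonised reading. The text states the transitions that apply after the first iUPD, and the table gives iSD only where iUPD is absent; if the text makes the time point iUPD, iSD is unavailable. Appendix 12 also says it is not an exhaustive guide, and Section 8.2.2 refers readers to an imaging manual that is not among the documents. This shows how a careful reader might resolve the conflict, but it requires setting aside the table's own condition that one of three listed findings be present, and an unchanged new lesion is none of them. The manual may settle the matter; the protocol as written does not.

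Several stronger inferences are tempting and are not supported:

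- *A growing new lesion is always scored stable and progression can never be confirmed.* Growth of 5 mm or more at the scan directly after iUPD is iCPD under Table 11-12. Target progression, non-target progression and additional new lesions still trigger iUPD.
- *The iPR sequence is also a contradiction.* It is a gap: the text supplies no competing label.
- *The iPR sequence costs 12 to 16 weeks.* That counts from week 20 to weeks 32 to 36, but the growth at week 20 would itself only be iUPD, so the loss is about 8 weeks.
- *Treatment automatically continues past progression.* Section 7.1 lists lack of clinical benefit as a reason to stop, and extension beyond cycle 6 requires no disease progression and agreement of the investigator and medical monitor.
- *The main analyses are biased.* Futility (Protocol Section 9.4.1.1) and the SAP response table (SAP Section 9.5.2) use RECIST 1.1, under which the new lesion is already progression. The SAP's efficacy methods contain no duration-of-response analysis, and SAP Section 7.1 records early termination. In the stable-target sequences the subject never responds, so no duration of response is overstated there.

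**Conclusion.** The inconsistency is real and narrow. For a new lesion that persists unchanged after iUPD, with targets stable and short of iPR, the text gives iUPD and Table 11-11 gives iSD. Under the table, later growth of that lesion cannot then be confirmed as iCPD. Separately, growth of a known new lesion after iPR has no place in Table 11-11 except iSD.

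The loss is of confirmation from that one lesion. Overall confirmation may be delayed: by one scan (4 to 8 weeks) or about 8 weeks in the sequences where another event later supplies it, and for as long as no other event occurs otherwise. How often such sequences arise cannot be estimated from the documents.

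The effect falls on site iRECIST assessments, iRECIST progression dates and best response, and the protocol's iRECIST duration of response in subjects with iPR. The conclusion rests on a literal reading of Table 11-11 and on the imaging manual not already resolving the point. No view is taken here on which classification is clinically right.

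**What to change.** Reconcile Table 11-11 with the text of Appendix 12 so that the same scans give one result:

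1. State one classification for a new lesion that persists unchanged after iUPD when the iCR and iPR criteria are not met. Leave intact the iPR row, which allows an unchanged persistent new lesion; a blanket rule that any persisting new lesion is iUPD would contradict it.
2. State how worsening of a previously recorded new lesion is classified after an iPR or iSD.
3. Make the iSD row consistent with both.
4. Carry the same wording into the imaging manual used by sites and the core laboratory.

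The cost is wording only, with no added scans or subjects. Depending on the choice made, some time points may move from iSD to iUPD or iCPD, so iRECIST reads made under the table should be checked against the settled rule before any iRECIST result is reported.

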9.4.2.2 Efficacy Analyses

Endpoint	Statistical Analysis Methods
Primary	Not applicable
Secondary	
Listings of secondary efficacy endpoints will be produced for all subjects in the dose-escalation cohorts and the dose-expansion cohorts.
 
The proportion of subjects with an objective response (per RECIST 1.1 and per iRECIST) and 95% CI will be tabulated by planned dose level using the RECIST Evaluable Analysis Set.
 
For all subjects treated at the MTD and/or RP2D, Kaplan-Meier methods will be used to estimate the time to event curve, median time to event and percentiles with 95% CI for 1) duration of response (RECIST 1.1 and iRECIST) 2) time to progression 3) PFS 4) OS. For all subjects treated at the MTD and/or RP2D, Kaplan-Meier methods will be used to estimate 6-month and 1-year PFS, 1-year and 2-year OS with 95% CI.

Exploratory	Will be described in the statistical analysis plan finalized before database lock.
--------------------	------------------------------------------------------------------------------------

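### Appendix 12 contradicts itself on whether responses before or without progression count under iRECIST; an iRECIST response rate built on iBOR would be biased downward

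*Protocol*

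**What the plan says.** Protocol Section 9.4.2.2 plans the secondary analysis: "The proportion of subjects with an objective response (per RECIST 1.1 and per iRECIST) and 95% CI will be tabulated by planned dose level". The same section plans Kaplan-Meier estimates of duration of response under both criteria.

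Appendix 12 (Section 11.12) then gives two sets of statements about iRECIST response.

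- *Responses before progression count.* The introduction says the two systems differ only in nomenclature until progression: "if a PR is identified at timepoint 2 for RECIST 1.1, this is called iPR at the same timepoint with the exact same measurements utilized". The closing paragraph on assessment methods adds: "For each subject at each timepoint, there is a separate RECIST 1.1 assessment and iRECIST assessment".
- *Responses count only after progression.* In Table 11-11 the rows for iCR, iPR and iSD each carry the line "Can only be assessed after the initial iRECIST iUPD time point (ie, the time point of RECIST 1.1 PD". Under Best Overall Response the rule is "iBOR is the best response seen since iUPD".

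The same list adds "iBOR does not require confirmation", whereas Protocol Section 8.2.2 says that PR and CR "require confirmation by a repeat consecutive assessment at least 4 weeks after the first detection of radiographical response".

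The SAP lists objective response per RECIST 1.1 and iRECIST among its endpoints (Section 2.1). It defines BOR and ORR for RECIST 1.1 only (Section 5, Appendix B) and tabulates only the RECIST 1.1 proportion (Section 9.5.2). Section 10 declares no changes from the protocol-specified analyses.

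**The concern.** The two sets of statements cannot both be followed. Take a subject whose tumour shrinks to PR at week 6 and who never progresses. Under the introduction this subject has an iPR. Under Table 11-11 the subject cannot have one, and under the iBOR rule there is no iUPD from which to start looking. A subject who responds, later progresses and does not respond again is in the same position.

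Appendix 12 gives its reason for adopting iRECIST as capturing late and durable responses that appear after RECIST 1.1 progression. An iRECIST rate should therefore add those responses to the ordinary ones. The iBOR rule, read literally, keeps the late responses and discards the ordinary ones. A programmer who wants an iRECIST counterpart to the SAP's RECIST 1.1 definition (the proportion with a best response of CR or PR) would find only iBOR to work from. At stake are the direction and size of the secondary iRECIST response rate, and which subjects enter the iRECIST duration-of-response analysis.

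**Working it through.** **Inputs.** The expansion size of 36, the illustrative response rate of 19% and its expected 95% CI of 8% to 36% come from Protocol Section 9.2. The exact Clopper-Pearson method comes from Section 9.4.2.1. The documents do not give the timing of responses relative to progression, so it is varied below.

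**The plan's own figure.** 19% of 36 is 6.84, so take 7 responders. For x of n, the exact limits are the 2.5% quantile of Beta(x, n − x + 1) and the 97.5% quantile of Beta(x + 1, n − x). For 7/36 = 19.4% this gives 8.2% to 36.0%, which reproduces the stated 8% to 36%.

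**Three counts for the same subjects.** Assume 7 RECIST 1.1 responders, all responding before or without progression. Let k of them also reach iCR or iPR after an iUPD, and let j further subjects respond only after an iUPD. Keep the denominator at 36 and set the confirmation question aside.

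- RECIST 1.1: 7/36
- iRECIST, literal iBOR rule: (k + j)/36
- iRECIST, counted from start of treatment: (7 + j)/36

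The literal rule falls short of the start-of-treatment count by (7 − k)/36, which is never negative, so the bias can only be downward. The literal rate is below the RECIST 1.1 rate whenever k + j < 7.

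**What the seven contribute under the literal rule (j = 0).**

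| k | Rate | Exact 95% CI |
|---|---|---|
| 0 | 0/36 = 0% | 0% to 9.7% |
| 1 | 1/36 = 2.8% | 0.1% to 14.5% |
| 3 | 3/36 = 8.3% | 1.8% to 22.5% |
| 5 | 5/36 = 13.9% | 4.7% to 29.5% |
| 7 | 7/36 = 19.4% | 8.2% to 36.0% |

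The upper limit in the first row can be checked by hand: 1 − 0.025^(1/36) = 0.097.

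**Adding late responders (k = 0).**

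| j | Literal iBOR rule | From start of treatment |
|---|---|---|
| 1 | 1/36 = 2.8% (0.1% to 14.5%) | 8/36 = 22.2% (10.1% to 39.2%) |
| 3 | 3/36 = 8.3% (1.8% to 22.5%) | 10/36 = 27.8% (14.2% to 45.2%) |

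**What does not move.** Futility in Protocol Section 9.4.1.1 uses objective response per RECIST 1.1, so the stopping guideline and its operating characteristics stand. The RECIST 1.1 rate uses SAP Appendix B. The primary endpoints are safety endpoints.

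**The case against.** A good part of the case on the other side stands.

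First, a reader might infer that a subject who responds before progression is, by rule, not an iRECIST responder. The documents do not support that as the single reading. The introduction calls such a response an iPR, and the closing paragraph provides an iRECIST assessment at every visit. Appendix 12 also describes iUPD as the point that starts application of iRECIST. On that view Table 11-11 describes only the phase after progression, and earlier responses carry over by name. This reading is coherent, but the table does not say it covers one phase only, and the iBOR sentence, which sets the window for best response, still excludes the earlier responses.

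Second, a reader might infer that the secondary iRECIST response rate is wrong. That needs a link from objective response to iBOR, and no section states one. The SAP produces no iRECIST rate at all, so no output it now plans is biased. What can be said is conditional: the rate is contradictorily defined in the protocol, and biased downward if iBOR is used.

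Third, 0/36 is one end of a range. It needs every responder to respond before any progression and nobody to respond after an iUPD.

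The appendix also says it is not exhaustive, and Section 8.2.2 refers to an imaging manual that is not among the documents. The manual might resolve the conflict, but the protocol would still contradict itself.

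**Conclusion.** The contradiction is established from the text. The introduction and closing paragraph of Appendix 12 count responses before progression; Table 11-11 and the iBOR rule do not. If objective response per iRECIST is derived from iBOR, the rate is biased downward and can fall below the RECIST 1.1 rate. On the protocol's illustration, the seven responders would contribute between 0/36 and 7/36, a loss of up to 19.4 percentage points.

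This rests on three assumptions: that iBOR would be used, that the denominator stays at 36, and that the protocol's 19% is a fair illustration. SAP Section 7.1 reports early termination, so 36 describes the plan rather than the data to expect.

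The point should be corrected because it concerns a listed secondary endpoint, but no stopping decision or primary endpoint depends on it. Two related gaps belong with it: the conflict over confirmation, and an iRECIST endpoint that the SAP lists but does not analyse while declaring no change from the protocol.

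**What to change.** 1. In Appendix 12, define iBOR, and objective response per iRECIST, as the best iRECIST timepoint response from start of treatment to end of tumour assessment. Include responses before the first iUPD and responses after an iUPD that has been reset.
2. In Table 11-11, delete the line restricting assessment to after the first iUPD from the iCR, iPR and iSD rows, so that CR, PR and SD before progression carry over as iCR, iPR and iSD.
3. Reconcile the statement that iBOR needs no confirmation with the four-week rule in Section 8.2.2. Without this, the corrected iRECIST rate could exceed the RECIST 1.1 rate merely by counting unconfirmed responses. Applying one confirmation rule to both rates would leave the handling of progression as the only difference between them.
4. In the SAP, either add the iRECIST response analysis with this definition (and the iRECIST duration of response that follows from it), or record in Section 10 that the iRECIST analysis has been dropped, and why.

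The cost is wording in one appendix, plus either a SAP definition with its outputs or a short entry in Section 10. No new data are needed: Section 8.2.2 and Appendix 12 already provide for assessment under both criteria.
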